- 10.1. Screening visit: Once informed consent is obtained, subjects may begin the screening process. If a study subject has been evaluated at VUMC by a study physician and has performed clinical testing that meets study guidelines within 30 days, then this testing maybe used to qualify for study entry. This will facilitate entry into the study, avoid repeated testing, and reduce costs. The following procedures will be performed at screening: 1) medical history and physical examination; 2) vital signs including oximetry; 3) blood chemistries, hematology counts; EBV and CMV serology 4) PFTs including spirometry, lung volumes, and diffusing capacity; 5) HRCT review; 6) surgical lung biopsy review; and 7) recording of current medications. If patients are not taking pirfenidone at the time of screening, then patients will be placed on pirfenidone and will be re-assessed to determine study eligibility 4 weeks later to allow ample time to determine tolerance to pirfenidone.
- 10.2. Enrollment visit: For subjects who meet eligibility criteria, enrollment may occur the same day as the screening visit. For subjects who require blood tests to be drawn at the screening visit, they will be notified by telephone of their eligibility for the study and study drug will be mailed to subjects by the investigational drug pharmacy. Randomization will be 2:1 valganciclovir versus placebo. Subjects will be offered the opportunity to undergo an optional research bronchoscopy. For subjects who undergo bronchoscopy, study drug will begin immediately following the bronchoscopy. Subjects who do not undergo bronchoscopy will begin study drug immediately. Additional tests that will be obtained are the following: 1) six minute walk test (6 MWT); 2) baseline blood chemistries and blood counts if >30 days after the screening visit; 3) baseline blood draws for biomarker and immunology studies, including HLA-typing; 4) teaching subjects self-monitoring and diary recording; and 5) optional bronchoscopy with BAL. Bronchoscopy will be the last test performed at enrollment.

- 10.3. Week 4 and 8 study visits: The primary purpose of these visits is to establish safety of study treatment and adherence to study treatment. Subject's diaries will be reviewed, medical history and physical examination will be performed, a pill count will be performed, current medications will be recorded, and chemistries and hematology counts will be obtained.
- 10.4. Week 12 study visits: This visit will conclude active treatment in the study and will be the primary endpoint for safety and tolerability. In addition, 6 MWT, and oximetry will be performed at this study visit. Subject's diaries will be reviewed, medical history and physical examination will be performed, PFTs will be obtained according to usual clinical care protocol, a pill count will be performed, current medications will be recorded, chemistries/hematology counts will be obtained, and blood will be obtained for biomarker and immunology studies. Subjects who consent to research bronchoscopy will undergo a second research bronchoscopy coordinated with the week 12 study visit.
- 10.5. Week 16 telephone call: 4 weeks after the final study visit (week 12), subjects will be contacted by telephone to review any side effects that occurred while taking study drug.
- 10.6. 6, 9, and 12 month visits: These visits will coincide with routine clinical care visits. Medical history and physical examination will be performed, and PFTs, 6MWT and oximetry will be performed according to usual clinical care protocol studies. A blood sample will be obtained for immunology studies.
- 10.7. Unscheduled disease progression visits: If a subject is found to have new symptoms or worsening of dyspnea or oxygen utilization, the subject will be scheduled for a clinic visit as soon as feasible to reassess secondary endpoints.
- 10.8. Table of Study Visits:

	Screening/ Enrollment Visit	Bronchoscopy Visit (optional)	Week 4 (study visit)	Week 8 (study visit)	Week 12 (study visit)	Week 16 (Teleph one call)	Month 6 (with clinical visit)	Month 9 (with clinical visit)	Month 12 (with clinical visit)
Consent	X								
Randomization	X								
Medical History	X				X				
Physical Exam	X				X				
Blood Chemistry (CMP; CBC, pregnancy test if applicable)	X		X	X	X				
Dispense study drug	X	(X)							
T cell studies from peripheral blood	X	(X)			X		X	X	X
Spirometry Test/DLCO	X				X		X	X	X
6 MWT	X				X		X	X	X

Bronchoscopy (if patient consents)		X			X				
Dispense Study/Review Study Diary for compliance evaluation	X		X	X	X				
Adverse Events			X	X	X	X	X	X	X

11. Data Collection for Specific Aims

11.1. Aim 1: To determine the safety and tolerability of oral valganciclovir as add-on therapy in patients with IPF tolerating standard treatment with pirfenidone.

11.1.1. Rationale: This study is designed to assess for safety and tolerability of valganciclovir in IPF patients who are taking standard therapy for IPF (pirfenidone) as assessed by type, frequency and duration of AE and SAEs. Exploratory secondary analysis to evaluate for clinical efficacy will include changes in FVC slope of patients with IPF, oxygenation, and exercise capacity. In addition to identifying whether anti-viral therapy could positively impact any of these parameters, collecting these data will ensure that any detrimental effects of the drugs used to treat herpesviruses on clinically relevant endpoints will be identified. Information will be collected as outlined below. For analysis of all these variables, the standard treatment arm with pirfenidone and placebo will be compared to valganciclovir and pirfenidone.

11.1.2. Evaluation for safety of valganciclovir. Assessment of safety will be determined by ongoing review of clinical laboratory tests (blood sampling for clinical laboratory parameters-see schedule of events), physical examination including vital sign measurements, functional status assessments and adverse events. Women of childbearing potential will undergo a urine pregnancy test at each study visit.

11.1.3. Evaluation for treatment emergent adverse events. A treatment-emergent adverse event (TEAE) is defined as a sign or symptom that emerges during treatment or within the 12 weeks following the last dose of the study drug, having been absent pretreatment or that has worsened relative to the pre-treatment state. Any adverse event deemed related to study drug will also be considered a TEAE regardless of elapsed time since last study drug dose. Adverse events will be graded using National Cancer Institute [NCI] CTCAE Version 3.0 during the study evaluation. Study drug-related adverse events will be listed individually.

11.1.4. Evaluation for change in pulmonary function. PFTs will be captured for all subjects using a CareFusion Sensormedics pulmonary function testing equipment (CareFusion, San Diego, CA), located in the VUMC pulmonary clinic. Measurements will be performed according to current ATS/ERS guidelines(46), and include spirometry (FEV1 and FVC) by NHANES, total lung capacity by body box plethysmography, and diffusing capacity of the lung for carbon monoxide (DLCO) all by %predicted according to Crapo(47). PFTs will be performed by registered respiratory technicians who are experienced in clinical trials. All registered respiratory technicians performing these measurements will be trained in this protocol. All subjects will perform measurements on one machine dedicated to the study to reduce variance.

11.1.5. Change from baseline in daytime resting oxygen requirements. Two measurements will be performed to determine if the research subject has a change in SpO2 or oxygen requirement at rest on each study visit. At each study visit, any supplemental oxygen will be removed for 5 minutes and SpO2 breathing ambient air will then be recorded and evaluated in comparison to baseline. In addition, the patient will have his/her supplemental oxygen requirement determined to maintain oxygen saturation $\geq 88\%$. The change in liters per minute flow rate in oxygen compared to baseline will be recorded.

11.1.6. Evaluation of exercise capacity. Exercise capacity will be determined on the basis of the 6 minute walk test (6MWT). The principal exercise capacity measurement will be the change in distance until SaO₂ reaches 80% from the 6MWT compared to baseline. The 6MWT will be performed using current guidelines(48). The walk is performed on room air throughout the study. Patients on supplemental oxygen will be off oxygen for a period of 10 minutes prior to initiation of the walk. Continuous finger pulse oximetry is performed during the test and the patient will walk at their own pace for as far as he/she can in the 6 minute duration. Measurements that will be collected include: 1) distance walked until SpO₂ reaches 88%; 2) time until SpO₂ reaches 88%; 3) distance walked to SpO₂ reaches 80%; 4) time until SpO₂ reaches 80%; 5) pre-test SpO₂; 6) post-test SpO₂; 7) lowest SpO₂ during test; and 8) total distance walked in 6 minutes; and 9) average velocity calculated as distance/time. In subjects who desaturate to <88%, an oxygen titration study will then be performed to determine exertional oxygen requirement. This value will be recorded and compared to baseline.

11.2. Aim 2: To investigate the effect of anti-herpesvirus treatment on changes in viral load and immune responses against herpesvirus.

11.2.1. Experimental design: Determination of herpesvirus DNA in BAL. BAL will be collected at bronchoscopy and the cell free portion will be used for determination of herpesvirus DNA. Total DNA will be isolated by the following procedure. After 10-fold concentration of cell free BAL fluid (10 ml), protein is digested overnight at 55°C in the presence of 500 µg/ml of proteinase K. DNA is then extracted with phenol/chloroform, followed by addition of 3 M sodium acetic acid (pH 6.5), precipitation in 100% isopropanol, and reconstitution in TE buffer. Real time qPCR amplification is performed on a StepOne Plus Real Time PCR machine (Applied Biosystems) to determine viral load based on a standard curve derived from a plasmid vector containing CMV or EBV DNA. Primer sequences used for CMV detection are as follows: (forward) 5'-TGA AGC GCC GCA TTG A-3', (reverse) 5'-TGG CCC GTA GGT CAT CCA-3'. Primer sequences used for EBV detection are as follows: (forward) 5'-CCC AAC ACT CCA CCA CAC C-3', (reverse) 5'-TCT TAG GAG CTG TCC GAG GG-3'. Results are reported as herpesvirus genomes per ml of BAL fluid.

11.2.2. Measurement of the anti-herpesvirus immune response. All patients will be HLA typed at the beginning of the study. Peripheral blood mononuclear cells (PBMCs) will be separated using standard Ficoll-Paque™ density centrifugation. Lymphocytes from peripheral blood obtained at baseline, 12 weeks (3 months), 6 months, 9 months, and 12 months and BAL obtained at baseline and 12 weeks will be studied. The following assays will be performed to quantify herpesviruses specific T-cell responses in subjects randomized to antiviral therapy or placebo:

11.2.2.1. As a marker of chronic immune activation in response to herpesvirus infection, we will evaluate PD-1 expression on naive, central memory (T_{CM}), effector memory (T_{EM}), and terminal effector memory (T_{EMRA}) populations using CCR7 and CD45RO to distinguish these memory T cell subsets. In addition, we will directly evaluate CD8+ T cell immune responses to herpesvirus antigens using MHC Class I tetramer assays. HLA-specific MHC-I CMV and EBV tetramers are available for individuals with HLA-A2, HLA-B7, HLA-B35, and HLA-B44 serotypes (Glycotope Biotechnology, Heidelberg, Germany), which comprises ~80% of the U.S. Caucasian population. Lymphocyte subsets will be separated by flow cytometry with anti-CD3 PerCPCy5, anti-CD8 FITC, anti-PD-1 Brilliant Violet 421, anti-CD45RO PECy5, and anti-CCR7 PE-CF594. CMV or EBV HLA class I tetramers conjugated with APC or Cy7 will be used for these studies (for example, HLA-A2/pp65 tetramers for CMV and HLA-A2/LMP1 tetramers; HLA-A2/LMP2 tetramers for EBV will be used for subjects with the HLA-A2 genotype). Live cells will be gated based on forward- and side-scatter properties, and analysis performed using FlowJo software (Tree Star, Ashland, OR), as previously described. All experiments will be acquired with an LSR-II flow cytometer (BD Biosciences), with a minimum of 30,000 events per sample. Detection of tetramer binding by flow cytometry will provide a specific signal to allow determination of the frequency of CMV- or EBV-specific CD8+ T cells in each sample, as well as the percentage of CMV- or EBV-specific CD8+ T cells expressing PD-1 within a given sample. Thus, the planned longitudinal

analysis will define the effects of antiviral therapy on CD8+ T cell populations in IPF patients, as well as determine the capacity for immunologic biomarkers, such as PD-1, to identify response to therapy.

11.2.2.2. While the studies described above will quantify differences in lymphocyte populations, we will also determine differences in lymphocyte activation in response to herpesvirus antigens. For these studies, PBMCs will be stimulated with pooled MHC Class I CMV- or EBV- specific peptides followed by flow cytometry with intracellular cytokine staining for IL-6, IL-2, and IFN- γ (49). Results will be reported as the percentage of CD8+ T cells that stain positive for each cytokine. As a positive control, cells will be stimulated with Staphylococcal enterotoxin B. In complementary studies, lymphocytes will be placed in 96-well plates (2×10^5 cells/well) and pooled MHC Class I CMV- or EBV- specific peptides will be added to cells in triplicate wells for measurement of cytokines, including Th1 cytokine (IL-2, IFN- γ and TNF α), Th2 cytokines (IL-4 and IL-10), and IL-6. Cytokine bead array (CBA) analysis will be performed on cell culture supernatants from untreated cells and MHC-I peptide-treated cells after 24 hours in culture as previously described. Together, these studies will determine functional differences in CD8+ T lymphocyte populations in response to herpesvirus antigens during the course of antiviral therapy.

11.2.2.3. Similar assays will be performed on lymphocytes isolated from BAL from each patient. The typical BAL sample contains $5-10 \times 10^6$ cells, of which 5-10% are lymphocytes. If cells are limiting, then tetramer assays and intracellular cytokine staining will be performed on PBMCs only.

11.3. Bronchoscopy: Individuals in the bronchoscopy substudy will undergo bronchoscopy at study entry and at week 12. Bronchoscopy will be performed using a standard protocol and will include airway survey, and BAL. For BAL, the bronchoscope will be wedged in the lingula or right middle lobe and 4 sequential aliquots of sterile saline (60 ml) will be instilled and gently withdrawn. Samples will be processed immediately. Bronchoscopy will be performed using standard monitoring procedures including continuous cardiac monitoring and blood pressure monitoring and pulse oximetry in the bronchoscopy suite at Vanderbilt University Hospital.

11.4. Biologic specimen management: Following bronchoscopy, BAL fluid will be centrifuged for collection of both the cell pellet and the supernatant. The supernatant will be aliquoted and stored at -70°C . Total and differential cell counts will be determined and remaining the remaining cell pellet will be used for flow cytometry studies. 50 ml of blood will be collected on the day of bronchoscopy, and peripheral blood mononuclear cells will be isolated using standard Ficoll-Paque™ density centrifugation. Plasma and serum will be aliquoted and stored at -70° .

12. Study drug procedures

Valganciclovir (Valgan) tablets and placebo will be provided by Genentech, Inc. through the VUMC pharmacy. The VUMC Pharmacy Investigational Drug Service (IDS) will dispense study medication at baseline and every 4 weeks coinciding with study visits. At the final study visit, subjects will return all unused study medication. To maintain blinding, valganciclovir and placebo will be encapsulated by the IDS as follows:

Starting Materials:

- 1) Valganciclovir 450 mg tablets or placebo
- 2) Microcrystalline cellulose
- 3) Size "0" orange caps
- 4) Capsule machine

Procedure:

- 1) Don appropriate attire for compounding
- 2) Fill capsules machine with empty capsules (tops removed)
- 3) Place one tablet in each empty capsule
- 4) Obtain verification from pharmacist
- 5) Cover with microcrystalline cellulose
- 6) Replace tops
- 7) Clean capsules with capsule cleaning towel
- 8) Package and label appropriately

9) Log in Investigational Drug Accountability Record

- 12.1. Contraindications, precautions, and side effects of study medications: Valganciclovir is FDA approved for the treatment and chronic suppression of herpesviruses, and has a good safety profile post marketing. The dose of valganciclovir recommended for this study is well within the FDA approved dosing range for other indications. The major side effect of valganciclovir is bone marrow suppression causing anemia, leukopenia, or thrombocytopenia. GI upset (nausea and diarrhea) is another reported side effect. These side effects will be monitored by routine laboratory testing and monitoring of subject diaries and direct questioning. Dose adjustments of valganciclovir are required for renal impairment, and dose modifications for renal insufficiency will be made according to recommended guidelines based on estimated creatinine clearance using the Cockcroft-Gault equation. For both valganciclovir and pirfenidone, there are no known major drug interactions requiring special clinical monitoring.
- 12.2. Valganciclovir safety and handling. In animal studies ganciclovir was found to be mutagenic, teratogenic, aspermatogenic and carcinogenic. Valganciclovir is considered a potential teratogen and carcinogen in humans with the potential to cause birth defects and cancers, and may cause temporary or permanent inhibition of spermatogenesis. Women of childbearing age will be required to use a medically approved means of contraception and will have urine pregnancy tests performed with each study visit. Male patients will be advised to practice barrier contraception during and for at least 90 days following treatment with valganciclovir. Tablets will not be broken or crushed. Since valganciclovir is considered a potential teratogen and carcinogen in humans, caution will be observed in handling broken tablets. Direct contact of broken or crushed tablets with skin or mucous membranes will be avoided. If such contact occurs, thorough washing with soap and water, and washing of eyes with sterile water will be performed. Unused medication will be returned to the pharmacy for disposal.

13. Data Management and Statistical Analysis Plan

- 13.1. **Data Management:** All data for this study will be stored in a password-protected, HIPAA security compliant computer database (REDCap). Vanderbilt was a founding member of the secure electronic REDCap database and houses much of this database on its servers. REDCap is a secure, web-based application designed to support data capture for research studies and registries. REDCap provides: 1) an intuitive interface for validated data entry; 2) audit trails for tracking data manipulation and export procedures; 3) automated export procedures for seamless data downloads to common statistical packages; and 4) procedures for importing data from external sources. Only study personnel for this project with appropriate permissions will be allowed to access the database. Authorized users can input data from anywhere in the world with secure web authentication and data logging. REDCap will be used for electronic capture of all data related to study visits with the exception of digital HRCT images. Data will be recorded directly from clinical records into REDCap by study personnel trained in this protocol. A second member of the study team will review the data for accuracy prior to the data being locked. This will avoid paper case report forms and any potential for breach of confidentiality from maintaining them or transposing data. All samples obtained for this study will be assigned a code which will not identify the subject. The only key to the code will be in the password-protected computer database. [name], PI of the study, will be responsible for maintaining confidentiality of data and codes. Only [name] and his delegates will have access to the code and information that identifies a participant as a being in this study. The results of analyses run on those samples will not be reported to the participant or clinical providers. No one else, including relatives, doctors, employers or insurance companies will be allowed to view the test results. Informed consent documents will be maintained in a locked file cabinet in the study coordinator's locked office. Only the study personnel will have access to this file cabinet.

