Randomization will be to pirfenidone plus placebo or pirfenidone plus valganciclovir. We prefer to have all subjects on pirfenidone as the standard of care for this study since the majority of patients elect to be treated with pirfenidone in our clinic. In addition, we anticipate valganciclovir will be better tolerated in combination with pirfenidone. We propose to enroll and randomize all eligible subjects with evidence of current or past EBV or CMV infection as determined by serologic testing for anti-EBV and CMV antibodies (total n=30) to treatment with pirfenidone plus valganciclovir (20 patients) or pirfenidone plus placebo (10 patients) for 12 weeks (**Fig. 1**). In order to maximize exposure to active treatment and assess for safety and tolerability, randomization will be 2:1 valganciclovir vs. placebo. The primary outcome will be safety and tolerability will be determined by type, frequency and duration of AE and SAEs. All study subjects will be offered bronchoscopy with BAL at study initiation and upon completion of treatment (12 weeks). Subjects will then be followed up at routine clinic visits at 6, 9 and 12 months for data collection.

[figure not shown]

Figure 1. Study flow chart.

6.2 **Rationale for Blinding and Placebo:**

6.1.1. A RCT is necessary given the clinical heterogeneity of IPF, and the inability to have two similar arms without randomization. A placebo arm will minimize bias since GI upset is a side effect of valganciclovir and standard treatment, pirfenidone. All subjects will be provided standard of care treatment to be applied equally across study groups as much as feasible and blinding will help avoid bias in the care provided.

6.1.2. Blinding is necessary to have optimal scientific validity, to make objective assessments of treatment effects, and to minimize dropout rates across study arms. In this study, there is particular concern that without blinding, subjects may opt to obtain off-label anti-viral therapy from non-study physicians if they become aware of the presence of herpesviruses in their lungs.

7. **Study population:** The study population will consist of male and female patients diagnosed with IPF, ages 21 and above, who are followed in the outpatient clinic setting.

7.1. **Inclusion criteria** will be:

- 7.1.1. age ≥ 21 and ≤ 80 years
- 7.1.2. ability to provided informed consent
- 7.1.3. diagnosis of probable or definite IPF according to ATS criteria(11)

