- 7.1.4. tolerance of full-dose (2403 mg/day) pirfenidone
- 7.1.5. Positive serology for EBV or CMV

7.2. **Exclusion criteria** will be:

- 7.2.1. FVC $\leq 40\%$ predicted
- 7.2.2. DLCO $\leq 35\%$ predicted (Crapo)
- 7.2.3. FEV1/FVC < 0.7
- 7.2.4. Significant centrilobular emphysema ($> 40\%$ by HRCT)

- 7.2.5. Active tobacco use (cigarette or cigar smoking)
- 7.2.6. Resting SpO₂ on room air <89%
- 7.2.7. listed for lung transplantation defined as being assigned a lung allocation score
- 7.2.8. environmental exposure (occupational, environmental, drug, etc.) felt by the principal investigator (PI) to be the etiology of the interstitial disease
- 7.2.9. diagnosis of collagen-vascular conditions (according to the published American College of Rheumatology criteria)
- 7.2.10. history of unstable or deteriorating cardiac disease
- 7.2.11. acute coronary syndrome, coronary artery bypass, or angioplasty within 3 months of screening
- 7.2.12. uncontrolled arrhythmia
- 7.2.13. uncontrolled hypertension
- 7.2.14. known HIV or hepatitis C
- 7.2.15. known cirrhosis or chronic active hepatitis
- 7.2.16. active substance or alcohol abuse
- 7.2.17. pregnancy or lactation
- 7.2.18. Women of childbearing potential who are not using a medically approved means of contraception. Subjects will be considered of childbearing potential if they are not surgically sterile or have not been postmenopausal for at least 2 years [any subject who is postmenopausal for < 2 years will be required to have a follicle-stimulating hormone (FSH) level to assess her potential to become pregnant
- 7.2.19. clinically relevant lab abnormalities (obtained within 30 days before enrollment), including:
 - 7.2.19.1. creatinine > 2 x upper limit of normal (ULN)
 - 7.2.19.2. hematology outside of specified limits: white blood cells (WBCs) < 3,500/mm³; hematocrit < 25% or > 59%; platelets < 100,000/mm³
 - 7.2.19.3. total bilirubin > 2 x ULN
 - 7.2.19.4. Aspartate (AST) or alanine aminotransferases (ALT) (serum glutamic-oxaloacetic; transaminase [SGOT], or serum glutamic pyruvic transaminase [SGPT]) > 2.0 x ULN
 - 7.2.19.5. alkaline phosphatase > 3 x ULN
 - 7.2.19.6. albumin < 3.0 mg/dL at screening
- 7.2.20. known hypersensitivity to study medication
- 7.2.21. any condition that, in the judgment of the PI, might cause participation in this study to be detrimental to the subject or that the PI deems makes the subject a poor candidate

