- 7.2.22. any therapy with immunosuppressants such as prednisone, azathioprine, or mycophenolate currently or anticipated to be needed during the study period (subjects on these drugs prior to the study will require a 30-day washout period before randomization)
- 7.2.23. participation in another IPF clinical treatment trial during the study period (if completing another IPF clinical treatment trial, then a 30-day washout period is required before randomization)
- 7.2.24. requirement for chronic suppressive therapy with valacyclovir for recurrent herpes virus infection
- 7.2.25. History of myelodysplasia, aplastic anemia, refractory anemia, or multiple myeloma.

8. Study Drug

- 8.1. *Dose justification of valganciclovir:* The standard dosing of valganciclovir for CMV disease when there is active pneumonitis with histopathologic changes such as intracellular inclusions, positive IHC, and acute inflammation is 900 mg twice daily(42). Typically, this occurs in solid organ or bone marrow transplant recipients, and is associated with viremia with viral loads in blood in the range of 10,000-100,000 viral genomes/ml(43). This dose is typically given for 21 days, and can be reduced 900 mg daily to further reduce low-grade viremia (200-2,000 copies/ml), and 900 mg/day can be given long term to prevent relapse or recurrent CMV disease(42). In IPF patients, CMV viral load in BAL is below 10,000 genomes/ml. Hence, the overall viral load is much lower in IPF patients compared to solid organ transplant recipients. Consequently, we believe a dose of 900 mg/day comparable to that used for chronic suppressive therapy in solid organ transplant recipients is most appropriate. A dose of 900

mg/day is generally well tolerated when administered for several months(42), and avoids the bone marrow suppression effects of long-term 900 mg twice daily dosing. Standard dosing of this regimen will be 900 mg once daily.

- 8.2. Justification of treating concomitant EBV and CMV with valganciclovir: Valganciclovir has activity against EBV and CMV. The 50% inhibitory concentration of valganciclovir against EBV is 1.5 mcg/ml(44), and the median area under the concentration versus time curve for 900 mg valganciclovir over 24 hrs (AUC₀₋₂₄) is 29 µg/ml with a peak concentration of 4.4 µg/ml(45). Hence the average concentration of valganciclovir is above the IC50 of EBV. We believe that monotherapy with valganciclovir should be effective and safe for subjects with CMV and EBV.

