- 8.3. Protocol for dosage adjustment: In subjects who develop a treatment-emergent, nonserious adverse events (i.e. nausea), valganciclovir will be administered in divided doses (450 mg twice daily). In subjects who develop treatment emergent clinically significant laboratory abnormalities possibly related to the study drug, study drug will be held until lab abnormalities have resolved. Current and new medication review will be conducted to assess for alternative contributors to lab abnormalities. After the treatment-emergent laboratory abnormality resolves, subjects will then resume study drug with repeat laboratory monitoring within 1 week after resumption of treatment, or earlier if symptoms recur in an earlier time period. If the treatment emergent laboratory abnormality recurs, study drug will be reduced to 450mg QD with close monitoring. If symptoms or lab abnormalities occur with 450mg QD, the study drug will be terminated.

9. Study Feasibility and Timeline

All subjects will be enrolled through the Vanderbilt Interstitial Lung Disease (ILD) clinics have been top enrolling sites for several multi-center clinical trials in IPF, and given this proven track record, we are confident we will meet enrollment targets. We will place priority on enrollment in this VICTR support pilot trial over industry-sponsored trials. We currently evaluate >200 new IPF cases per year in our clinics. At the present time, approximately 125 IPF patients are being treated with pirfenidone in the Vanderbilt ILD clinic, and the majority of these patients should be eligible for this study. We expect to begin recruiting patients immediately upon approval of this study and complete enrollment within 9 months such that subjects will reach the primary study endpoint by the end of Year 1. Ongoing ascertainment of data collected during routine clinical follow-up of these study subjects will then be completed in Year 2.

10. Study Visits

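### The fixed dose steps in 8.3 conflict with the renal dose modification in 12.1: read literally, the nausea step raises the daily dose of any subject on a renally reduced dose

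*Combined protocol and SAP*

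**What the plan says.** All references are to the combined protocol and SAP.

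- **Entry (7.1.1, 7.2.19.1).** Eligible ages are "age ≥ 21 and ≤ 80 years". The only renal exclusion is "creatinine > 2 x upper limit of normal (ULN"). No creatinine-clearance limit is given.
- **Renal dosing (12.1).** Dose adjustment is required in renal impairment: "dose modifications for renal insufficiency will be made according to recommended guidelines based on estimated creatinine clearance using the Cockcroft-Gault equation". Neither thresholds nor reduced doses are stated.
- **Standard dose (8.1).** "Standard dosing of this regimen will be 900 mg once daily".
- **Dose adjustment for events (8.3).** For non-serious events such as nausea, "valganciclovir will be administered in divided doses (450 mg twice daily"). For a clinically significant laboratory abnormality possibly related to study drug, "study drug will be held until lab abnormalities have resolved", and drug is then resumed. Next, "If the treatment emergent laboratory abnormality recurs, study drug will be reduced to 450mg QD with close monitoring". The section ends: "If symptoms or lab abnormalities occur with 450mg QD, the study drug will be terminated".
- **Counting (13.2.1, 13.3, 14).** A dose reduction, or an interruption followed by resumption, is not a withdrawal. Discontinuation due to adverse events is compared between arms by chi-square. Withdrawals due to adverse events also drive the interim stopping rule in section 14.

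Sections 8.3 and 12.1 do not refer to each other. Section 8.3 makes no exception for a subject whose dose has already been modified for renal function.

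**The concern.** The two sections can apply to the same subject at the same time. Section 12.1 sets a dose below standard because clearance is low. Section 8.3 then responds to an adverse event with amounts that assume the subject is on 900 mg/day. Followed as written, a rule meant to improve tolerability would raise exposure in someone with reduced clearance who is already having an adverse event.

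There is also a consequence for the endpoint. Where 8.3 can be read either as hold-and-resume or as termination, the same clinical course can be recorded as a non-withdrawal or as a primary-endpoint event, depending on which sentence site staff apply. With 20 and 10 subjects per arm, one subject matters.

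**Working it through.** **1. Can subjects with low clearance enter?** Cockcroft-Gault for men is clearance = (140 − age) × weight / (72 × creatinine); for women, multiply by 0.85. The age limit and the 2 × ULN limit come from the protocol. ULN and weight are not given and are assumed. With ULN 1.2 mg/dL, creatinine at the limit is 2.4 mg/dL and the denominator is 72 × 2.4 = 172.8.

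| Man at the entry limit | Calculation | mL/min |
|---|---|---|
| 60 years, 90 kg | 80 × 90 / 172.8 | 42 |
| 70 years, 80 kg | 70 × 80 / 172.8 | 32 |
| 75 years, 70 kg | 65 × 70 / 172.8 | 26 |
| 80 years, 60 kg | 60 × 60 / 172.8 | 21 |

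The 80-year-old, 60 kg man ranges from 25 mL/min (ULN 1.0) to 19 (ULN 1.3). Over ULN 1.0–1.5, ages 60–80 and weights 60–100 kg, the values at the limit are about 17–56 mL/min in men and 14–47 in women.

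**2. What does 8.3 do to a reduced dose?** 450 mg × 2 = 900 mg/day, which exceeds every daily dose below 900 mg. That needs no outside figure. The two lower rows below use illustrative renal doses that the documents do not state. Section 12 puts one whole 450 mg tablet in each capsule, and 12.2 forbids breaking tablets, so a lower average dose would mean dosing less often than daily.

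| Dose under 12.1 | Nausea or similar | First laboratory abnormality | Recurrence |
|---|---|---|---|
| 900 mg/day | 900 mg/day, unchanged | hold, resume | down to 450 mg once daily |
| 450 mg once daily (assumed) | 900 mg/day (× 2), or terminate | hold and resume, or terminate | 450 to 450, no reduction, or terminate |
| 450 mg every other day, mean 225 mg/day (assumed) | 900 mg/day (× 4) | hold, resume | up to 450 mg once daily (× 2) |

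The double entries in the middle row arise because the last sentence of 8.3 attaches termination to symptoms or laboratory abnormalities at 450 mg once daily, without saying how that dose was reached.

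**3. Does the classification matter?** First, the plan's own power figure: 25% versus 0%, 20 versus 10 subjects, one-sided alpha 0.1. The pooled rate is 5/30 = 0.167. The null SE is √(0.167 × 0.833 × 0.15) = 0.144, and the alternative SE is √(0.25 × 0.75 / 20) = 0.097. Power = Φ[(0.25 − 1.282 × 0.144) / 0.097] = 0.749, which matches the stated 75%.

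On the same one-sided scale, with 0/10 on placebo:

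- 2/20: pooled 0.0667, SE √(0.0667 × 0.9333 × 0.15) = 0.0966, z = 0.10 / 0.0966 = 1.035, p = 0.150.
- 3/20: pooled 0.10, SE √(0.10 × 0.90 × 0.15) = 0.1162, z = 0.15 / 0.1162 = 1.291, p = 0.098.

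One subject moves the result across 0.1. Section 13.3 does not say whether the chi-square is corrected or one-sided. With Fisher's exact test the crossing lies between 5/20 (p = 0.109) and 6/20 (p = 0.065), again one subject.

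**The case against.** The strongest defence is that 8.3 should be read in context. Dividing the dose describes splitting the 8.1 regimen, not increasing a smaller one. Section 12.1 separately requires renal modification, section 14 leaves dose modifications to the investigators, and 7.2.21 lets the PI exclude unsuitable candidates. Sensible clinicians would probably not raise the dose. This mitigates the gap but does not close it. Section 16.2 requires strict adherence and bars the investigator from altering procedures, 7.2.21 governs entry and not later dosing, and nothing in 8.3 yields to 12.1.

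A reader might infer four stronger points, which the documents do not support:

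- *That the creatinine entry limit is itself an error.* It is not. An entry limit in creatinine with dosing by clearance is workable, and 12.1 expects such subjects. The limit shows only that the conflict can arise.
- *That the laboratory rule ends treatment at the first event in renally reduced subjects.* This needs a renal dose of exactly 450 mg once daily, which is not stated. It also needs the last sentence of 8.3 to override the hold-and-resume sentence. That last sentence directly follows the recurrence step and may be meant only for subjects who reached 450 mg that way.
- *That 8.3 offers nothing below 450 mg once daily.* Hold, medication review and resumption do not depend on dose.
- *That the comparison between arms is biased.* Allocation is randomised and double-blind, so renal function is balanced in expectation. The documents do not show how many subjects would be affected.

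**Conclusion.** The concern holds as a conflict between 8.3 and 12.1. That the nausea step, read literally, raises any renally reduced daily dose follows from the protocol's own figures. Two parts are conditional. At an assumed renal dose of 450 mg once daily, 8.3 gives incompatible instructions for nausea and for a first laboratory abnormality. At an assumed lower dose, its recurrence step becomes an increase. The clearance values rest on assumed ULN and weights, and they describe subjects at the entry limit, not typical ones. The effect on the primary endpoint is an ambiguity in how a subject is counted. It could decide the result at one-sided 0.1 if the count falls near the boundary, but it is not a demonstrated bias.

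**What to change.** Reconcile 8.3 with 12.1 so that a subject on a renally adjusted dose has one unambiguous sequence for non-serious events, first laboratory abnormalities and recurrences, with each section referring to the other. Add weight and calculated Cockcroft-Gault clearance to the screening items in 10.1 and 10.8; 12.1 already needs both. State in 13.2.1 and 13.3 how stops in these subjects count in the primary endpoint, and apply the same definition to the section 14 stopping rule. The doses, cut-offs, eligibility limit and stopping steps are for the sponsor to decide.

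The cost is protocol wording and one calculation. Age and creatinine are already available at screening; weight is not listed there by name.
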